### Primary objective:

To evaluate the effect of a LiPA intervention on arterial stiffness in individuals with T2D.

### Secondary Objective(s):

Next to its associations with cardiovascular health, physical activity has been positively associated with numerous other outcomes including microvascular function, favourable metabolic health, body composition, quality of life, physical and mental health. Therefore, these health outcomes are included as secondary end points.

To investigate the feasibility of a LiPA intervention program in the reduction sedentary time and increase in standing and stepping time obtained by the activPAL.

To investigate the effect of a LiPA intervention program on microvascular function.

To investigate the effect of a LiPA intervention program on metabolic health.

To investigate the effect of a LiPA intervention program on body composition.

To investigate the effect of a LiPA intervention program on quality of life.

To investigate the effect of a LiPA intervention program on depressive symptoms.

To investigate the effect of a LiPA intervention program on immune cells.

### **3. STUDY DESIGN**

This study is a single-blinded randomized controlled trial (enrollment via block randomization (block size of 4)). The duration of the study is 12 months; a 6-month intervention with a 6 month follow-up period to examine both the long-term health effects of the intervention as well as any long-term compliance to the intervention.

Study measurements of all participants will take place at baseline (month 1 (t = 0)), month 3 (t = 3), month 6 (t = 6), and month 12 (t = 12) at the Maastricht UMC+.

Participants in the intervention group will be instructed to increase their LiPA by decreasing sedentary time. Participants will follow 4 workshops in group sessions on strategies to change their behaviour and will receive a feedback physical activity monitor that will be worn continuously on the wrist and provide e-feedback on activity behaviour. During the COVID-19 crisis the workshops temporarily are offered online. The intervention procedures are described in more detail in section 5.

Participants in the control group will receive 4 workshops in group sessions on healthy lifestyle including information and strategies to increase LiPA and reduce sedentary time similar to the intervention group, but will not receive a feedback-activity monitor.

### 3.1 Duration

The total duration of the study is 3 years. The duration of the RCT is 12 months.

The intervention period is 6 months with a 6-month follow-up.

Expected starting date for the study: quarter 4, 2016

Expected starting date for enrolment participants: quarter 1, 2017

Expected date finished enrolment participants: quarter 1, 2018

Expected date end of follow-up: quarter 1, 2019

Statistical analyses and report of the results: quarter 3, 2019

### 3.2 Evaluations by visit

An overview of the procedures and examinations are shown in table 1. All participants (both the intervention and the control group) will be invited to the research centre at t=0 (baseline visit at month 1); at t=1 (first investigational visit at month 3), at t=2 (second investigational visit at month 6); and at t=3 (third investigational visit at month 12) at the Maastricht UMC+.

#### Screening

A preliminary screening will be carried out by telephone interview in order to decide whether the participant is eligible for the study (see section 4.2 and 4.3 for the in- and exclusion criteria). The participant will then be invited for the baseline visit, which starts with the informed consent procedure (please see appendices for informed consent) and an explanation of this very first baseline visit. The baseline namely consists of two parts. Part A is strictly part of the inclusion procedure. During this part a standard physical examination will take place and an ultrasound scan will be performed to screen for large atherosclerotic plaques of the carotid arteries (see below). If then the participants is indeed eligible part B will take place in which the investigational baseline measurements are performed. After the above procedure randomization will take place. From then on participants will run through the protocol either being part of the intervention or control group.

#### Measurements at the four investigational visits (t = 0, 3, 6 and 12)

- sociodemographic data
- medical history & medication use: by means of an interview
- lifestyle factors (alcohol use and smoking behaviour), quality of life, depressive symptoms – by means of questionnaires
- Sedentary and physical activity monitoring: by means of the activPAL® activity monitor for 7 days

- venous sampling (approx. 40 ml per person per visit; 8 collecting tubes of 5 ml) for fasting glucose, fasting insulin, HbA1c, lipid profile, creatinine, albumin and biomarkers of endothelial dysfunction (vWF, s-VCAM-1, sE-selectin, sTM, SICAM-1), low-grade inflammation(CRP, SAA, IL-6, TNF-alfa, IL-8) and immune cells. The remainder of the material will be stored in a biobank for future determination of any potentially interesting (bio)markers on the topic of physical activity. For any such future procedures further approval will be sought from the METC/MUMC+.
- Anthropometric data (height, weight, waist and hip circumference and bio-electrical impedance measurements)
- vascular measurement (arterial stiffness, microvascular function and blood pressure)
- physical function measurements (grip strength and timed chair test)

Table 1 Overview of the study procedures

	Screening	Baseline	Intervention						Follow-up
Time point (months)		0	1	2	3	4	5	6	12
Eligibility									
Informed consent									
Randomisation									
Examinations									
Intervention group									
Workshop, group session									
Continuous activity monitoring									
Biweekly feedback on activity by phone									
Monthly feedback on activity by phone									
Control group									
Workshop									

**4. STUDY POPULATION**

**4.1 Population (base)**

Basically all community-dwelling individuals with type 2 diabetes are eligible for participation in the current trial taking into account the in- and exclusion criteria described below.

Participants will therefore be drawn from the community with the help of public advertising and targeted recruitment with the help of general practitioners and nurse practitioners. In addition, participants will be drawn from the out-patient diabetes clinic from the Maastricht UMC+.

For both the intervention and control group an equal sex- and age distribution is aimed for. It is estimated that recruitment is achievable within the proposed timeframe because of the potential large number of eligible participants (total number of estimated of number of patients with type 2 diabetes within the Maastricht UMC+ region approx. 12.000 of whom approx. 2/3 will be eligible).

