### 4.2 Inclusion criteria

In order to be eligible to participate in this study, a subject must meet all of the following criteria:

- 40-70 years old
- having type 2 diabetes
- BMI 20-35 kg/m^2
- having a sedentary lifestyle (i.e., self-reported moderate-to-vigorous physical activity < 150 minutes per week)
- willingness to undergo randomization
- being in the possession of personally owned smart phone

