### **6.1.3 Other study parameters**

Individual patient characteristics: age, sex, ethnicity, level of education, employment status, medical history and medication use.

A process evaluation of LiPAT will give insight into the reach, implementation, and satisfaction of the intervention program. Research questions for the process evaluation are:

- Who participated in the intervention and who dropped out?
- Was the intervention executed as planned?
- How did participants experience the intervention and specifically the workshops and the use of Fitbit inspire and the mobile application?

A partially structured interview at the end of the intervention (month 6) with all participants and the research nurse will be carried out to capture their experiences with LiPAT. The following aspects will be covered during the interviews; some items are only relevant for the intervention group (e.g. the use of the Fitbit inspire). This process evaluation is based upon Moore, GF et al. BMJ 2015.

Dose delivered (for the intervention and control group)

1. Extent to which the research nurse:
  - a. informed the participant about the risks of a sedentary lifestyle and the benefit of LiPA
  - b. collaboratively set goals and set up an action plan with the participant
  - c. gave feedback based on the general physical activity goals
  - d. discussed with the participant barriers and facilitators for being active

Fidelity

1. Extent to which LiPAT was implemented as planned by the participant?
2. Have the participant and research nurse perceived any technical problems with the Fitbit inspire device? (for intervention group only)
3. Have the participant and research nurse experienced any technical problems with the mobile application? (for intervention group only)

Dose received (exposure)

1. Overall opinion of the participant regarding engagement in the intervention program
2. Instruction of the Fitbit inspire and the mobile application (use of the manual and the instruction)(for intervention group only)

Dose received (satisfaction)

1. Experience with LiPAT
  - a. Activity monitoring
  - b. Workshops
  - c. Feedback messages
2. Experience with the mobile application (for intervention group only)
  - a. Goal setting
  - b. Activity monitoring
  - c. Feedback messages

3. How satisfied were the participants and the research nurse with the intervention program – workshops and LiPAT?
4. How did the participants perceive the outcomes and relevance of the interventions?

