### **6.2 Randomisation, blinding and treatment allocation**

Randomisation by the research staff will take place during the baseline visit (please see above) with / via block randomization in a block size of 4 (Suresh, KP. J Hum Reprod Sci. 2011).

Participants will be randomly assigned in Ldot, a web-based tool, designed to monitor study logistics, to the LPA intervention group or the control group.

Randomisation will be stratified according to sex to ensure an equal distribution of men and women in both groups.

This is a single-blind design. To ensure blinding, participants will be instructed to not discuss their assigned intervention during any of the trial visits with the research nurse or vascular technician performing any of the trial measurements.

The participants in the intervention group will be asked not to wear their Fitbit inspire device on trial visit days and will be reminded not to do so via the web interface.

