## **8. STATISTICAL ANALYSIS**

The significance levels used in the statistical analyses will be 0.05. The validity of the normality assumption will be checked for all outcomes. Baseline characteristics will be compared between the intervention and the control group. For continuous variables (e.g. age, BMI) mean and standard deviations will be presented; numbers and percentages will be shown for categorical variables (e.g. smoking, medication use). T-tests will be used to compare differences in continuous baseline characteristics between the intervention and control group and chi-square test will be used for categorical variables. Assuming that the randomization was successful no differences are expected. Missing data will be imputed using multiple imputations techniques.

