### **8.1 Primary study parameter(s)**

The effect of the intervention on the primary outcome PWV at month 6 will be analysed using intention-to-treat (ITT) approach according to randomization assignment. The ITT analyses will be used as primary method for our statistical analyses and any outcomes in our reports will be primarily based upon these ITT analyses. In addition, a per protocol analysis will be performed for those who attended the workshops. These analyses will be used to gain some insights into any potential non-response / drop out. These per protocol analyses will not be the primary source for reporting outcomes. General linear models will be used to analyse the effect of the intervention on PWV at month 6. Due to the COVID-19 crisis some month 6 measurement will take place at a later moment, depending on the duration of this delay we will have to adjust for this in our statistical analyses. In addition, repeated measures will be taken into account, baseline, month 3, and month 6 using mixed models in SPSS. The 3-month visits might be missing for some participants due to COVID-19 crisis, we assume that the 6-month measurements for these participants can take place as planned. In these models, subject is entered as a random effect and intervention (categorical variable with 2 levels: 1: intervention; 2: control group) as a fixed effect. The baseline value of PWV and sex will be used as covariates in analyses.

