### **8.2 Secondary study parameter(s)**

Sedentary time, as measured by the activPAL will be analysed as total sedentary minutes on an average day as well as the percentage of sedentary during wake time. Similarly, time standing and stepping, also derived from the activPAL data will be analysed. All metabolic health parameters and microcirculation measurements will also be analysed as continuous

variables. Quality of life and mental functioning are also analysed as continuous variables. Finally, measures of body composition measures are also all continuous outcomes variables

Similar to the primary outcome analyses, general linear mixed models will be used to analyse the change in the secondary outcome measures from baseline to month 6. Using mixed models, the repeated measures will be taken into account similar to the analyses with the primary outcome.

All analyses, for the both primary and secondary outcomes will also be conducted for the follow-up (month 12 data) to examine the long-term effect of the intervention, taking into account all repeated measures (baseline, month 3, month 6) in a mixed model.

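### Age is named for balance between the arms and is already collected, but is not a covariate, so a small and nearly free gain in precision goes unused

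*Protocol*

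**What the plan says.** Section 4.1 names two characteristics on which the arms should be alike: "For both the intervention and control group an equal sex- and age distribution is aimed for".

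Section 6.2 gives a mechanism for one of them. Allocation uses "block randomization in a block size of 4", and "Randomisation will be stratified according to sex to ensure an equal distribution of men and women in both groups". Age has no corresponding provision.

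Section 8.1 fixes the adjustment for the primary outcome: "The baseline value of PWV and sex will be used as covariates in analyses". Section 8.2 carries the approach to the other outcomes and names no further covariate: "Similar to the primary outcome analyses, general linear mixed models will be used to analyse the change in the secondary outcome measures".

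Age will be available. Section 6.1.3 lists "Individual patient characteristics: age, sex, ethnicity, level of education, employment status, medical history and medication use", and section 4.2 admits participants "40-70 years old". In the analysis, age appears only in the baseline comparison of section 8: "For continuous variables (e.g. age, BMI) mean and standard deviations will be presented", with a t-test between the arms.

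**The concern.** The protocol treats sex and age alike when it states what should be balanced, then handles them differently. Sex is both stratified and adjusted for; age is neither. If the arms differ in age by chance, and age predicts month-6 PWV beyond what baseline PWV and sex already explain, that part of the outcome stays in the residual and widens the interval somewhat.

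What is at stake is precision. There is also a minor practical point: the protocol attaches no consequence to the baseline t-test on age. Naming age in advance avoids having to decide about adjustment after the arms have been compared.

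**Working it through.** **1. Is age used anywhere beyond description?** Setting the sections side by side:

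| Section | Sex | Age |
|---|---|---|
| 4.1 balance aim | yes | yes |
| 6.2 stratification | yes | no |
| 8.1 covariates | yes | no |
| 8.2 models | as 8.1 | not added |
| 8 baseline comparison | categorical variables, chi-square | named, t-test |

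No other section stratifies, minimises or adjusts for age.

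**2. The target effect in SD units.** Section 4.4 gives 73 per group for a 10% difference at two-sided alpha 0.05 and 80% power, but no mean or SD of PWV. The 73 therefore cannot be reproduced directly and is solved backwards:

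- standardised difference = (1.960 + 0.842) × √(2/73) = 2.802 × 0.1655 = 0.464
- implied SD/mean = 0.10 / 0.464 = 0.216

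**3. Chance imbalance in age with 80 per arm.**

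- SE of the difference in means = √(2/80) = 0.158 SD
- 95% chance range = ±1.96 × 0.158 = ±0.31 SD
- For an assumed age SD of 6 to 8.66 years (the upper value is a uniform spread over 40-70, 30/√12), this is about ±1.9 to ±2.7 years.

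**4. Precision gained by adding age.** The input is the partial correlation of age with month-6 PWV, given baseline PWV and sex. The protocol does not give it, so 0.1 to 0.2 is assumed. Residual variance is multiplied by 1 − r²:

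| Partial r | Variance factor | Interval width factor (√) | Narrowing |
|---|---|---|---|
| 0.1 | 0.99 | 0.995 | 0.5% |
| 0.2 | 0.96 | 0.980 | 2.0% |

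The cost is one degree of freedom. With 10% dropout there are 72 completers per arm, 144 in all. The month-6 model already has four parameters (intercept, arm, baseline PWV, sex), which leaves 140. The variance cost is about 140/139 = 1.007, or 0.7%. The net factors are 0.99 × 1.007 = 0.997 and 0.96 × 1.007 = 0.967.

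**5. Shift in the estimate from an extreme imbalance.** Assume a baseline-to-month-6 PWV correlation of 0.6. The residual SD after baseline adjustment is √(1 − 0.36) = 0.8 of the outcome SD. An imbalance of 0.31 SD in the part of age not already explained by baseline PWV and sex would move the estimate by:

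- r = 0.1: 0.31 × 0.1 × 0.8 = 0.025 SD; 0.025 / 0.464 = 5%
- r = 0.2: 0.31 × 0.2 × 0.8 = 0.050 SD; 0.050 / 0.464 = 11%

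These are values at the edge of the 95% range; a typical imbalance is smaller.

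**6. Power on the same assumptions.** With 72 per arm, the implied SD and a baseline correlation of 0.6, power is 93.6% without age. It is 93.8% (r = 0.1) or 94.4% (r = 0.2) with age, ignoring the degree of freedom.

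**The case against.** The strongest reply is that nothing here is wrong. Section 4.1 states a soft aim and promises neither stratification nor adjustment. Randomising 160 people balances age in expectation, and section 8 says that no baseline differences are expected if randomisation succeeds. Adjusting for the stratification factor and the baseline outcome is a coherent, standard choice. Section 8.1 does not call its list exclusive, and a statistical analysis plan, which is not shown, may add prognostic covariates. Every correlation used above is assumed. Most of this stands, and it is why the point is only an optional improvement.

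Three stronger readings are tempting, and the protocol supports none of them.

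- *The result will be biased by age.* Chance imbalance after randomisation is not bias, and the standard error already reflects it.
- *The possible distortion is large.* A reader could reach a large share of the target effect by multiplying the imbalance by a raw age-PWV correlation. That describes a model without baseline PWV, and section 8.1 already includes it.
- *Adding the covariate fulfils the aim of section 4.1.* A covariate leaves the age distribution of each arm as it is. Only recruitment or allocation could make the distributions more alike.

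What remains is that the protocol itself singles out age as worth balancing, will have the value for every participant, and does not use it where it could help.

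**Conclusion.** The point holds as a minor, optional improvement. Age is named alongside sex in section 4.1, but only sex is stratified, and only baseline PWV and sex are named as covariates. The primary analysis is valid as written.

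The expected gain is small: about 1-4% of residual variance, or an interval 0.5-2% narrower, less about 0.7% of variance for the extra parameter. At the low end of the assumed range the net gain is close to nil. The figures depend on an assumed partial correlation of 0.1-0.2, an assumed baseline-to-month-6 correlation of 0.6 for the shift and power figures, and a 0.46 SD target solved backwards from 73 per group. They apply to PWV only. The protocol gives no basis for a figure on the secondary outcomes.

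**What to change.** In section 8.1, add age at baseline, as a continuous variable, to the prespecified covariates beside baseline PWV and sex. State in section 8.2 that the same covariate is carried to the secondary-outcome models. Leave the sex-stratified blocks of section 6.2 unchanged.

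The cost is a few words and one degree of freedom per model, with no new data. The text should present this as adjustment for chance age imbalance and should not claim that it makes the age distributions equal. If the sponsor prefers not to adjust, rewording section 4.1 so that it no longer singles out age would also bring the sections into line, without the gain in precision.

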### 4.2 Inclusion criteria

In order to be eligible to participate in this study, a subject must meet all of the following criteria:

- 40-70 years old
- having type 2 diabetes
- BMI 20-35 kg/m^2
- having a sedentary lifestyle (i.e., self-reported moderate-to-vigorous physical activity < 150 minutes per week)
- willingness to undergo randomization
- being in the possession of personally owned smart phone

### 4.3 Exclusion criteria

A potential subject who meets any of the following criteria will be excluded from participation:

- not being able to walk for 15 minutes for any (medical) reason
- currently engaged in an (medical) exercise program
- plan to move out of the study area in the next 12 months
- (*digital*) illiteracy or being unable to read Dutch
- a history of any cardiovascular event (including stroke) three months prior to possible inclusion
- a history of signs or symptoms of ischemic heart disease and(or) heart failure three months prior to possible inclusion
- a history or signs or symptoms of peripheral arterial disease three months prior to possible inclusion
- a history or signs or symptoms of severe diabetic neuropathy or diabetic foot ulcers three months prior to possible inclusion
- a history of sign or symptoms of severe diabetic retinopathy three months prior to possible inclusion
- a history or sign or symptoms of severe osteoarthritis or severe joint complaints three months prior to possible inclusion

- a history or signs or symptoms of COPD (eligible are those participants with a COPD Gold classification  $\leq$  I)
- uncontrolled diabetes (i.e., uncontrolled hypo- or hyperglycaemia)
- uncontrolled hypertension (i.e., systolic / diastolic blood pressure  $\geq$  180 / 95 mmHg)

### 4.4 Sample size calculation

For the primary objectives of the study:

to be able to detect a 10% difference in PWV after the intervention between the intervention group and the control group set against a probability of a type 1 error at 0.05 (i.e.,  $\alpha$ ) and the ability to detect a true difference between the intervention group and the control group set at 80% (i.e.,  $\beta$ ) both groups should consist of a minimum of 73 participants each. These estimates are conservative taking into account only PWV values at entry and exit of the trial. The 10% difference is speculative and based upon a mean PWV estimates from The Maastricht Study data as there is currently no data available on LiPA and arterial stiffness. For reasons of efficiency in addition to potential drop (roughly estimated at 10%) out we will include in each group 80 participants

to be able to detect a 10% difference in carotid distensibility after the intervention between the intervention group and the control group set against a probability of a type 1 error at 0.05 (i.e.,  $\alpha$ ) and the ability to detect a true difference between the intervention group and the control group set at 80% (i.e.,  $\beta$ ) both groups should consist of a minimum of 73 participants each. These estimates are conservative taking into account only carotid distensibility values at entry ( $t = 0$ ) and exit of the investigational period of the trial ( $t = 6$ ). The 10% difference is speculative and based upon mean estimate from The Maastricht Study data as there is currently no data available on LiPA and arterial stiffness. For reasons of efficiency in addition to potential drop (roughly estimated at 10%) out we will include in each group 80 participants.

